### **5.8 Concomitant Medication**

Concomitant medication documentation will begin as soon as the subject takes the first dose of study medication. All concomitant medications used through the end of the study will be recorded. The dates of administration, dosage, and reason for use will be included. Subjects will be allowed to continue on concomitant medications. Any study related side effect (e.g., nausea) requiring medication management must be approved by the investigator prior to consumption.

## **6 STUDY PROCEDURES**

### **6.1 Visit 1 Screening Visit/Baseline/Randomization (can occur on same day)**

- Signing an informed consent form prior to any study related activities
- Confirmation of Atrial Fibrillation either at admission or in subjects medical history
- Physical exam including vitals
- Body weight and height
- Review MRI results to determine diagnosis of TIA or determine size of Ischemic stroke
- Review of labs, echocardiogram, and EKG reports or draw labs and conduct EKG/ECHO if needed.
- Obtain medical history with demographics
- Schedule carotid ultrasound or CTA angiogram of the neck if not done at admission
- Schedule TEE if not done at admission (optional)
- Review of concomitant medications and procedures
- Obtain mRS, NIHSS and SS-QOL scales
- Urine pregnancy test (for women of childbearing potential)
- Review of all inclusion/exclusion criteria
- Treat any patient with hypertension according the current guidelines. (see section 5.2)

### **6.2 Randomization**

- Confirm subject group selection based of the SACC recommendations, (TIA, Small ischemic stroke, Medium ischemic stroke) and must confirm subjects meets all inclusion criteria and no exclusion criteria prior to randomization.
- Randomize Subject
- Discuss treatment arm with patient

### **6.3 Drug Initiation (may be same as randomization depending on group and study arm)**

- Urine pregnancy test if not done within 24 hours of this visit
- Dispense study medication

- Provide patient education regarding treatment regimen.
- Apply event monitor within 14 days from randomization
- Assess AE/SAE's
- Assess concomitant medication changes
- Schedule next visit
- INR for Warfarin arm

#### 6.4 Treatment visits

Visit day 14 (+/-3)

- Physical exam
- Vital Signs
- Urine pregnancy test if required
- ECG
- NIHSS, mRS
- MRI or CT scan
- INR for Warfarin arm
- Assess Drug Compliance
- Dispense study medication
- Provide patient education
- Assess AE/SAE's
- Assess concomitant medication /procedure changes
- Schedule next visit

Visit day 30 (+/-5) and 90 (+/- 10)

- Physical exam
- Vital Signs
- Collect Laboratory assessments including INR for Warfarin arm
- Urine pregnancy test if required
- ECG
- NIHSS and mRS
- SS-QOL only at day 30
- Assess Drug Compliance
- Dispense study medication
- Provide patient education
- Assess concomitant medication /procedure changes
- Assess AE/SAE's
- Schedule next visit

Visit day 60, 120, 150 (+/- 10)

- Physical exam
- Vital Signs
- Collect INR for Warfarin arm
- Urine pregnancy test if required
- ECG
- NIHSS , mRS

- Assess Drug Compliance
- Dispense study medication
- Provide patient education
- Assess concomitant medication /procedure changes
- Assess AE/SAE's
- Schedule next visit

#### **6.5 End of Study (+/- 10)**

- Physical exam
- Vital Signs
- Collect Laboratory assessments including INR for Warfarin arm
- Urine pregnancy test if required
- MRI or CT scan
- ECG
- NIHSS ,mRS and SS-QOL
- Assess Drug Compliance
- Provide patient education
- Assess concomitant medication /procedure changes
- Assess AE/SAE's
- Start on non-study Anticoagulation therapy

#### **6.6 Early Withdrawal (EW)**

- Physical exam
- Vital Signs
- Collect Laboratory assessments including INR for Warfarin arm
- Urine pregnancy test if required
- MRI or CT scan
- ECG
- NIHSS ,mRS and SS-QOL
- Assess Drug Compliance
- Provide patient education
- Assess concomitant medication /procedure changes
- Assess AE/SAE's
- Start on non-study Anticoagulation therapy

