## Schedule of Study Procedures

TIA -Apixaban group	Screen/ Baseline	Treatment Initiation	Maintenance ‡						End of Study	30day PC	Early Withdrawal	Unsch
			3	4	5	6	7	8				
Visit Number	1	2	3	4	5	6	7	8	9	10		
Study Days (Visit Window)	0	$\beta$ (See also table 2)	14 ( $\pm 3$ )	30 ( $\pm 5$ )	60 ( $\pm 10$ ) )	90 ( $\pm 10$ ) )	120 ( $\pm 10$ ) )	150 ( $\pm 10$ ) )	180 ( $\pm 10$ )	210 ( $\pm 10$ ) )		
Informed Consent	✓											
Inclusion/Exclusion Criteria	✓											
General Medical History/Demographics	✓											
Physical Exam	✓		✓	✓	✓	✓	✓	✓	✓		✓	✓
Vital Signs §	✓		✓	✓	✓	✓	✓	✓	✓		✓	✓
mRS	✓		✓	✓	✓	✓	✓	✓	✓		✓	
NIHSS	✓		✓	✓	✓	✓	✓	✓	✓		✓	✓
SS-QOL	✓			✓					✓		✓	✓
Urine pregnancy test †	✓	✓ †	✓	✓	✓	✓	✓	✓	✓		✓	
12-lead ECG	✓		✓	✓	✓	✓	✓	✓	✓		✓	✓
Clinical Lab Evaluation*	✓ **			✓		✓			✓		✓	✓
PT/INR ( Warfarin arm only)		✓	✓	✓	✓	✓	✓	✓	✓		✓	✓
TEE	✓ †											
Event Monitor (prior to DC)		✓										
Carotid Ultrasound	✓											
MRI or CT scan	✓		✓						✓		✓	
Record AE/SAEs		✓	✓	✓	✓	✓	✓	✓	✓	✓	✓	✓
Prior and con. medications/procedures	✓	✓	✓	✓	✓	✓	✓	✓	✓	✓	✓	
Dispense Study Drug		✓	✓	✓	✓	✓	✓	✓				✓
Drug Compliance			✓	✓	✓	✓	✓	✓	✓		✓	✓
Non-study anticoagulation initiation									✓		✓	

$\beta$  drug initiation will be as follows: TIA: Apixaban arm day 0-3/Warfarin arm day 7( $\pm 5$ ): Small stroke: Apixaban arm day 3-5/Warfarin arm day 14( $\pm 5$ ): Medium stroke: Apixaban arm day 7-9/Warfarin arm day 14( $\pm 5$ )

\* Results of existing tests will be obtained from subject's hospital chart to assess eligibility. If tests results are not available labs will be performed at the visit. See section 6 for a detailed description of what this entails.

§ Vitals: BP, HR,, weight, (RR and Temperature are optional, height obtained at baseline only)

\*\* Labs for inclusion/exclusion criteria will include CMP, CBC with diff and platelets, Creatinine, PT/INR, LFTs and Lipid panel.

† performed prior to discharge

† All WOCBP MUST have a negative pregnancy test within 24 hours before receiving apixaban. The minimum sensitivity of the pregnancy test must be 25 IU/L or equivalent units of HCG. If the pregnancy test is positive, the subject must not receive apixaban and must not be enrolled in the study. † Study day at screening is day of event

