## 5.4 End of Study

A final visit will be conducted at day 180 in person. Study medication will be collected at this visit and the patient will be started on standard of care therapy. Decisions regarding anticoagulation will be based off the subject's individual needs as assessed by the Principal Investigator or Sub-Investigator.

30 days after the EOS a phone call will be made to assess for AE's or SAE's that may have occurred during that time frame.

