## 5.7 Subject Completion/Early Withdrawal

It will be documented whether or not each subject completed the clinical study. A subject is considered to have completed the study if he/she has taken all study medications for 6 months and has completed 6 month study assessments or withdrew from the study due to the occurrence of a recurrent embolic stroke, hemorrhagic transformation or death. If a subject does not complete the treatment phase, their data will be used for efficacy and for any safety analysis.

It is understood that withdrawals may occur during a trial. Each subject has the right to withdraw from the trial at any time for any reason without affecting the right to treatment by the investigator. Subjects who do not complete the treatment phase for other reasons then mentioned above, should be followed at day 14 and EOS visits, if possible. At minimum these patients should have a monthly phone call to assess AE/SAE and vital status if they are unable to continue follow-up in clinic.

Subjects needing to withdraw prior to the completion of the study and who do not agree to continue in follow-up should return to the clinic for completion of early withdrawal procedures, as outlined in table 1.

Reasons that a subject may discontinue the study include the following:

- Adverse events including recurrent stroke or hemorrhagic transformation
- Intercurrent illnesses
- Any significant new medical condition
- Protocol violation
- Non-compliance to study medication regimen

- Use of any investigational drug other than the study medication
- Intake of prohibited medication
- Pregnancy
- Subject withdrew consent or lost to follow-up
- Other (reason to be documented)

Withdrawals due to intercurrent illnesses or AEs will be fully documented in the CRF with the addition of supplementary information if available and/or appropriate. Withdrawals due to non-attendance will be followed-up by the investigator to obtain the reason for non-attendance.

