#### For individual patients

In the event of a Grade 3 or higher adverse event attributable to treatment with APIXABAN and not related to the underlying disease, administration of APIXABAN will be suspended in the patient to allow analysis and determination whether to continue the treatment, alter dosing regimen or to exclude the patient from further participation in the study; if there is any increase in cerebral microbleeds (CMB) at day 14, in either arm, all study medication will be suspended until a repeat MRI is performed 48 hours from day 14 MRI. Study medication will be restarted in clinically stable individuals. In subjects who have a CT scan at day 14 and have a asymptomatic intracranial hemorrhage, all study medication will be suspended until a repeat CT is performed at 48 hours from the day 14 scan. Sstudy medication will be restarted in clinically stable individuals. If subjects experience any symptomatic hemorrhagic transformation in either arm, study medication will be suspended. All subjects will continued to be followed up monthly either by phone or clinic contact until the end of study.

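### The exit checklists and schedule start non-study anticoagulation without condition, which does not match section 5.4 and leaves no rule for early withdrawal or for patients suspended after symptomatic hemorrhagic transformation

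*Combined protocol and SAP*

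**What the plan says.** Sections 6.5 and 6.6 are the procedure lists for the End of Study and Early Withdrawal visits. Each closes with the same item, "Start on non-study Anticoagulation therapy". The Schedule of Study Procedures has a row "Non-study anticoagulation initiation", ticked at those two visits with no footnote or condition.

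Section 5.4 describes the final visit at day 180. It says that "the patient will be started on standard of care therapy", and then: "Decisions regarding anticoagulation will be based off the subject's individual needs as assessed by the Principal Investigator or Sub-Investigator".

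Section 5.7 includes in its reasons for discontinuing "Adverse events including recurrent stroke or hemorrhagic transformation". It sends to the early-withdrawal procedures those patients who withdraw and do not agree to further follow-up.

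Section 7.5.2, under the rules for individual patients, says: "If subjects experience any symptomatic hemorrhagic transformation in either arm, study medication will be suspended". It also keeps all subjects in monthly contact until the end of the study. It does not mention non-study anticoagulation.

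**The concern.** Sites tend to work from visit checklists and the schedule, and that is where the unconditional wording sits. A site that follows 5.4 makes an individual decision at day 180; a site that follows 6.5 carries out a listed procedure. At early withdrawal the checklist is the only instruction there is.

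The gap matters most for a patient whose study anticoagulant was suspended because of a symptomatic intracranial bleed. Nothing exempts that patient from the exit item, so a literal reading has a second anticoagulant started at the exit visit.

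There is a lesser consequence for the analysis. Endpoints run from randomization to 180 days (7.1), patients are analysed by randomized assignment (8.1.4), and data from those who do not complete treatment are used (5.7). Where outcomes are still observed after an early exit, treatment that varies with the passage a site happened to follow could bear on later ischemic, fatal or bleeding events in either arm.

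**Working it through.** No arithmetic applies. The question is whether the passages give one consistent instruction for each exit route.

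1. **Is the item conditional?** Not in 6.5, 6.6 or the schedule row. The same lists can carry a condition when one is written, as in "Urine pregnancy test if required". Both lists also include a brain scan at the same visit, but do not link the anticoagulation item to its result.

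2. **Day-180 visit: 6.5 against 5.4.** Section 6.5 and the End of Study tick list a procedure to be done. Section 5.4 makes it an investigator decision based on the patient's needs. These are different instructions for the same visit. The mismatch is softened because 5.4 also says that standard of care will be started.

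3. **Early withdrawal: 6.6 against 5.4.** Section 5.4 is confined to day 180, so it does not contradict 6.6. What is missing is any sentence that makes anticoagulation at early withdrawal an individual decision. The defect here is an absent rule beside an unconditional item.

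4. **Suspended patients: 6.5 and 6.6 against 7.5.2.** Section 7.5.2 suspends study medication after symptomatic hemorrhagic transformation and states no restart for that case. For a day-14 increase in microbleeds on MRI, or an asymptomatic hemorrhage on day-14 CT, it does provide for restart, after a repeat scan and in clinically stable patients. The exit item concerns a non-study drug, on which 7.5.2 is silent. The two texts can both be obeyed to the letter, but the result is that one anticoagulant is suspended and another begun with no stated condition.

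5. **Which exit visit would such a patient reach?** Section 7.5.2 keeps the patient in monthly contact to the end of the study. Section 5.7 reserves the early-withdrawal visit for those who decline follow-up, but it also counts withdrawal for hemorrhagic transformation as having completed the study, and directs its day-14 and end-of-study follow-up to patients who stop for other reasons. The route is therefore unclear. Since 6.5 and 6.6 carry the same line, either route leads to the same item; only at day 180 does 5.4 stand beside it.

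**The case against.** The strongest reply is that the checklists are summaries of visits, not orders that override the body of the protocol. Section 6.4 lists dispensing of study medication at day 14 with no condition, although 7.5.2 suspends it for any increase in microbleeds found at that visit. So a missing qualifier does not prove that an item is meant for every patient, and the line in 6.5 can be read as shorthand for 5.4. This has force at day 180. It does not help at early withdrawal, where there is no fuller passage for the line to abbreviate.

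A reader might infer that the checklists contradict 7.5.2 outright, so that a patient with hemorrhagic transformation is given two opposite orders. The documents do not support that: 7.5.2 governs study medication and says nothing about other anticoagulants. Nor do the checklists state that patients withdrawn for hemorrhagic transformation are included; that follows only from the absence of an exception. Many such patients would stay in follow-up and reach the day-180 visit, where 5.4 applies.

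The effect on the results can also be overstated. A patient who leaves because of an intracranial bleed already has the secondary outcome, and patients attending the 6.6 visit have declined follow-up, so few later events would be captured. Later fatal or ischemic events could still count where they are ascertained.

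Finally, 5.8 already records concomitant drugs with dates, dosage and reason for use, so what was given at exit is largely documented.

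**Conclusion.** The plan is wrong as written, as an internal inconsistency. The unconditional item in 6.5 and the End of Study tick do not match 5.4. For early withdrawal, and for patients suspended under 7.5.2 after symptomatic hemorrhagic transformation, no passage says how the item applies. With 7.5.2 the conflict is one of effect, not of words.

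No numerical size can be given. A reader might set all early exits treated under the checklist against none under 7.5.2, but the first figure only restates the literal reading and the second extends the suspension to drugs that 7.5.2 does not mention. Nor does the trial-wide trigger of five symptomatic transformations on apixaban bound the number affected, since it counts bleeds in one arm and not exits from the study.

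The conclusion assumes that sites may apply the checklist and schedule as written. If every site read them as subordinate to 5.4, the day-180 mismatch would have little practical effect, but the gap at early withdrawal would remain. The point deserves correction because it concerns anticoagulation after intracranial bleeding and costs almost nothing to put right; it does not call the trial's design into question.

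**What to change.** Reconcile 5.4, 5.7, 6.5, 6.6, 7.5.2 and the schedule row into one rule that covers every exit route, including exit or suspension for hemorrhagic transformation. The sponsor's clinicians choose the rule; none is proposed here. Then replace the unconditional line in 6.5 and 6.6, and the two schedule ticks, with a reference to that rule.

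Optionally, add to the exit case report form the reason for not starting anticoagulation. Drugs started, with dates, are already captured under 5.8.

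The cost is protocol wording and at most one form field, with no extra visits or patients.

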### **7 STUDY ENDPOINTS AND EVALUATIONS**

#### **7.1 Primary Endpoint**

Endpoint data will start at randomization up to 180 days. These composite endpoints include:

- Fatal stroke
- Recurrent Ischemic stroke
- New hemorrhagic stroke

## 7.2 Secondary Endpoints

- Any intracranial bleeds assessed by MRI/CT scan at day 14 and EOS or at outcome event.
- Any major bleeds defined as clinically overt bleeding that was accompanied by one or more of the following: a decrease in hemoglobin of 2 g/dL or more; a transfusion of 2 or more units of packed red blood cells; bleeding that occurred in at least one of the following critical sites: intracranial, intraspinal, intraocular, pericardial, intra-articular, intramuscular with compartment syndrome, retroperitoneal; or bleeding that was fatal. Intracranial hemorrhage included intracerebral (hemorrhagic stroke), subarachnoid, and subdural bleeds.

## 7.3 Other Endpoints of Interest

- Understanding the natural progression of ischemic stroke patients with NVAf within the first 14 days status post initial stroke event (i.e. stroke or TIA)
- Effect of the addition of anti-epileptic medications during hospital admission on outcomes in patients with embolic stroke secondary to AF
- Factors attributing to the addition of anti-epileptic medications during hospital admission in patients with embolic stroke secondary to AF
- Factors affecting stroke specific quality of life in patients with embolic stroke secondary to AF

## 7.4 Baseline Evaluation (see also schedule of events)

### 7.4.1 Physical Examination

A complete medical history including demographic characteristics (age, gender, and race/ethnicity) will be collected at screening. Complete physical and neurologic examinations will be performed at screening

### 7.4.2 Vital Signs

Heart rate, blood pressure will be performed at every study visit (temperature, and respirations are optional)

### 7.4.3 Laboratory Evaluations

Evidence of clinical laboratory evaluation within 72 hours of hospital admission will be required at screening. This will include Creatinine (CPT 82575), complete metabolic panel (CPT 80053), complete blood count with differential and platelets (CPT 85025), Lipid Panel (CPT 80061) and PT/INR (CPT 85730), urine HCG (CPT 81025) if indicated, aPTT (CPT 85730), TSH (CPT 84443)

All WOCBP MUST have a negative pregnancy test within 24 hours before receiving apixaban. The minimum sensitivity of the pregnancy test must be 25 IU/L or equivalent units of HCG. If the pregnancy test is positive, the subject must not receive apixaban and must not be enrolled in the study. In addition, all WOCBP should be instructed to contact the investigator immediately if they suspect they might be pregnant (e.g., missed or late menstrual period) at any time during study participation.

See schedule of events

## 7.5 Efficacy and Safety Evaluations (see also schedule of events)

### 7.5.1 Diagnostic Tests, Scales, Measures, etc.

*MRI w/o contrast (GRE sequencing preferred but all effort should be used to maintain the same modality of sequencing and magnet strength from baseline or CT w/o contrast –*

Will be performed, along with the NIHSS, to measure the size of ischemic stroke at screening. It will also be used for follow-up assessments to indicate any early hemorrhagic transformation or micro-embolic strokes. Patients who are unable to have a MRI due to contraindication (i.e. implantable pacemaker) will have be allowed to use CT with the NIHSS.

- TIA- will have no ischemic changes
- Acute infarcts are classified as small, medium or large based on size of the largest ischemic lesion:
  - small = lesion in the anterior or posterior circulation <1.5 cm.
  - medium = equal to or greater than 1.5cm but less than a complete territory infarct lesion in a cortical superficial branch of the anterior cerebral artery (ACA), middle cerebral artery (MCA), posterior cerebral artery (PCA), or in a branch of MCA or PCA, or lesion in internal border-zone territories.
  - large posterior = lesion involving complete PCA territory, or lesion of cerebellum 1.5 cm or larger or any lesion of the brain stem.
  - large anterior = lesion involving complete ACA or MCA territory, or lesion involving >1 artery territory
- All classifications are based of the measurement of the largest lesion size.

*TEE-*

Will be obtained or scheduled prior to discharge on all patients or will be scheduled as part of their evaluation for potential cardiac sources of emboli. In addition to imaging specifically of left atrium thrombus; measurements will be obtained for left atrial size, left atrium appendage, velocity, left ventricle size and function and other significant myocardial or valvular heart disease.

*Carotid ultrasound-*

Will be performed on all patients to rule out ipsilateral carotid disease during the screening visit.

*Laboratory evaluations-*

Will be obtained from all patients at screening, day 30, day 90 and day 180. Additional lab measurements for the warfarin group will be obtained monthly and at unscheduled visits if warranted by the warfarin dosing protocol.

*Event Monitor-*

Will be obtained on all patients in order to characterize the atrial fibrillation burden to assess potential relationship to outcome events. The event monitor be started within 14 days (+3) from randomization and maintained for 30 days.

*NIH Stroke Scale (NIHSS)- see appendix 13.2*

Will be used with all patients to provide a rate of worsening, i.e., progression of the index stroke event assessed by deterioration in clinical symptoms and/or an increase in the score on the NIHSS. The NIHSS is a 15-item neurologic examination stroke scale used to evaluate the effect of acute cerebral infarction on the levels of consciousness, language, neglect, visual-field loss, extraocular movement, motor strength, ataxia, dysarthria, and sensory loss. The total score can range from 0-42. The breakdown of the scoring is described below:

0 = no stroke

1-4 = minor stroke

5-15 = moderate stroke

15-20 = moderate/severe stroke

21-42 = severe stroke

This scale will be administered at screening/baseline, day 14, 30, 60, 90, 120, 150, 180, and early withdrawal.

*Modified Rankin Scale (mRS)- see appendix 13.1*

Will be used with all patients to measure severity of stroke and overall disability of patients, this scale will also administered on screening/baseline, day 14, 30, 60, 90, 120, 150, 180, and early withdrawal. The breakdown of scoring is described below:

Scale	Disability
0	No symptoms at all
1	No significant disability despite symptoms ; able to carry out all usual duties and activities
2	Slight disability; unable to carry out all previous activities, but able to look after own affairs without assistance
3	Moderate disability; requiring some help, but able to walk without assistance
4	Moderately severe disability; unable to walk without assistance and unable to attend to bodily needs without assistance
5	Severe disability; bedridden, incontinent and requiring constant nursing care and attention
6	Dead

*Stroke Specific Quality of Life Scale (SS-QOL)-See appendix 13.3*

The SS-QOL is a self-report questionnaire consisting of 49 items in the 12 domains of energy, family roles, language, mobility, mood, personality, self-care, social roles, thinking, upper extremity function, vision, and work/productivity. The domains are scored separately, and a total score is also provided. The psychometric properties of the SS-QOL have been validated in patients with ischemic stroke and intracerebral hemorrhage.

*Physical*

Weight will be recorded in pounds (lb) and height in inches (in).

Physical examination will include assessment of the head, eyes, ears, nose, throat, heart, chest, lungs, abdomen, extremities, peripheral pulses, skin and any other physical conditions of note.

*Vital Signs*

Blood pressure will be measured in all subjects in either the sitting or supine position.

*Pregnancy Testing*

Sexually active Women of Child-Bearing Potential (WOCBP) must use an effective method of birth control during the course of the study, in a manner such that risk of failure is minimized.

Before study enrollment, WOCBP must be advised of the importance of avoiding pregnancy during study participation and the potential risk factors for an unintentional pregnancy. The subject must sign an informed consent form documenting this discussion.

*Electrocardiogram (ECG)*

12-lead ECG recordings will be obtained from primary care or performed at screening and examined for gross abnormalities. ECGs will be conducted at various points throughout the study as shown in section 5

*Clinical Laboratory Evaluations*

The following labs will be obtained at varies time points in the study as shown in section 6.

Complete metabolic panel which includes liver enzymes and creatinine, complete blood count with differential and platelets, PT/INR and if indicated urine HCG

